Protocol

Title: Percutaneous Interruption of the Coracohumeral Ligament for the treatment of Frozen Shoulder.

Authors: [REDACTED]

Principal Investigator:

[REDACTED]
Montefiore Medical Center.

Clinical Study Protocol

Type of study/Study design: Prospective double Arm randomized control trail. Cross over at one month from non-interventional arm (LA) to intervention arm (TENEX).

Background Significance:

Chronic inflammation of the shoulder joint capsule and its associated structures can lead to clinically significant symptoms, including insidious onset of pain, and ultimately restricting range of motion. Although the underlying mechanism for adhesive capsulitis (AC) is not well defined, some studies suggest that fibroblast proliferation and thickening of the coracohumeral ligament (CHL) is a proposed mechanism for which AC and subsequent prolonged immobilization and symptoms present (1, 2, 3). Other studies suggest that it is due to a combination of capsular fibrosis and inflammation within the synovium, and other focus on the fact that thickening of the CHL is responsible for limiting external rotation in patients affected by adhesive capsulitis (1).

AC coined frozen shoulder by Codman in 1934 [2], has an estimated prevalence of 2-3% in the general population, with ages 40-70 affected most commonly, and predominantly women. While the precise etiology remains undefined, it can be secondary to trauma or an idiopathic etiology and has been found to have an incidence as high as 20% in diabetic patients, with worse functional outcomes when compared to non-diabetic patients. Hypothyroidism and cerebrovascular disease have also been shown to be associated with an increased risk of developing AC (4). AC is typically a clinical diagnosis. However, both magnetic resonance and ultrasonography have consistently shown thickening of the CHL (1). Several studies have compared arthrographic evidence of findings in adhesive capsulitis, and many reported a thickening of the CHL in cases of frozen shoulder as compared to control subjects (2). In a study implementing shear-wave elastography (SWE), the CHL in patients diagnosed with adhesive capsulitis was thicker and stiffer (4).

Interventions aimed at improving AC and CHL damage, clinical symptomatology, as well as histopathological findings range from rest and physical therapy, local injections and hydrodilation, to advanced surgical interventions (4, 5). These surgical options include manipulation under anesthesia (MUA) and arthroscopic capsulotomy. MUA is an aggressive mobilization of the joint in an effort to lyse adhesions and to stretch the contracted glenohumeral capsule. Despite potential benefits, MUA has been associated with superior labral anterior and posterior (SLAP) lesions, bankart lesions, capsular tears, hemarthrosis, and even humeral or glenoid fractures (4). Arthroscopic capsulotomy allows for direct visualization of the CHL and confirmation of the diagnosis of AC, and several studies have shown improvement in pain relief as well as range of motion (4). However, patients who did not benefit from this intervention were women, typically over the age of 50, with a past medical history of diabetes mellitus. CHL resection has also been described as a potential treatment option for AC (6, 7), with current therapy limited to a surgical approach. Management of refractory disease through arthroscopic capsular release has been shown to improve pain and increase range-of-motion (8, 9, 4). A sequela of arthroscopic surgery is postoperative persistent AC, which some surgeons attempt to prophylactically prevent with adequate postoperative pain control so that the patient can participate in a physical therapy program. The potential limitations of current conservative management and

Given the significance of CHL hypertrophy in AC, the authors believe lesioning this pathologic ligament will result in significant improvement for patients suffering from AC. Our cadaveric technical analysis added to the clinical safety trail by the This study aims to use sonographically guided percutaneous sectioning of coracohumeral ligament for the treatment of AC. This novel technique is minimally invasive, and we present our findings with proof of concept for a clinical technical treatment of the CHL in patients with frozen shoulder. The patients we will be recruiting will

be subjects who have failed the conservative treatment and are not surgical candidates. They will be informed of the risks and the procedure and take informed consent.

Study Objective:

The objective of this study is to use sonographically guided percutaneous interruption of the Coracohumeral ligament for the treatment of refractory Adhesive Capsulitis. We have already performed this procedure in cadavers and will validate the cadaveric findings in human subjects.

Study Design:

Patient will be identified by the Co-PI (██████████) for screening. He will then determine whether the patient is an appropriate non-surgical candidate. If the subject is an appropriate non-surgical candidate, he/she will be then referred to the PI (██████████). ██████████ will then screen the patient for participation in the study. He will then inform the research staff, who will approach the patient in the clinic for possible participation in the study.

The research staff will then explain the procedure, risks and possible benefits of the procedure. PI (██████████) will also explain the procedure as he will be performing the procedure. After informed consent is taken the patient will then be enrolled in the study. They will then undergo the procedure. Of note, this procedure will only be performed on Wednesdays when ██████████ is physically present on the same floor of the Hutchinson campus. He will not be in any other surgery when the patient is undergoing the procedure with ██████████ will thus be available for any assistance.

This is a study where patients will be randomized to two groups. One group will receive Local anesthetic and Tenex. The second group will receive local anesthetic only. The second group will be given the option of crossing over to local anesthetic and Tenex group at 1-month visit. Please note Local anesthetic is standard of care for diagnostic purposes. Both groups will be receiving the same anesthetic.

Subjects shoulder ROM, QOL, VAS and opioid usage will be assessed before and after the procedure in both the groups. These parameters will also be evaluated at the 1-month visits.

Other relevant data will be collected through chart review. This includes patient medical, surgical history, medication history, other health conditions, demographics and exercise/physiotherapy sessions.

Primary outcomes: Improvement in shoulder range of motion (ROM) (external rotation) immediately post procedure by at least 100%

Secondary outcomes:

Sustained ROM at 1-month visit compared to pre-procedure ROM

Opioid use before after and at 1-month visit

VAS scale for an expected difference of 3 points

Quality of life questionnaire before procedure, after procedure and at 1-month visit.

Bilateral shoulder ROM improvements in subjects with bilateral procedure

Target Population: 57 adult patients will be enrolled in the Montefiore Hutchinson campus.

Power Analysis:

Assume 30% of patients in the local anesthetic group will have at least a 100% improvement in range of motion one-month post treatment. With a sample size of 32 patients in the Tenex group and 16 patients in the local

anesthetic group, the study will have 81.9% power to detect a difference of 45% in patients with at least a 100% improvement in range of motion between the Tenex group and local anesthetic group one-month post treatment using a two-sided Fisher's exact test at a 0.05 significance level.

Assume an attrition rate of 15%, 57 patients will be enrolled and randomized in a 2:1 ratio to receive either Tenex or local anesthetics.

Randomization

Block randomization was done using SPSS software by the in house statistician. Randomization is noted at the end of the document for all our patients. Please note randomization is 2:1 Tenex:LA. LA will cross over to Tenex at 1 month if the subjects desire.

Inclusion:

1. Adults >18 and <89 years
2. Established Diagnosis of Adhesive capsulitis (AC)
 - Ligament Flavum >3mm, diagnosed by US evaluation
 - decreased shoulder ROM in external rotation and abduction (50% of unaffected side) (17)
3. Patients who have tried other conventional therapies like steroid treatments, surgical treatments, physiotherapy with little (defined by less than 20 degrees improvement in shoulder ROM – external rotation) to no improvement in the shoulder ROM

Exclusion:

1. Patients with AC but showing improvement in shoulder ROM progressively (defined by improvement in ROM > 200 external rotation or 20 degrees per week when undergoing physiotherapy)
2. Patients who are currently pregnant
3. less than 18 years old and older than 89 years old

Patient recruitment:

Patients will be identified by the PI/Co-PI and will be consented, screened and enrolled into the study by the approved research staff at the Montefiore Hutchison campus.

Informed consent:

All the subjects will be consented before enrolling into the study. A detailed informed consent is taken by the approved research staff who will explain the study in detail with regards to risks and benefits. The patient can refuse to be a part of the study at any point even after signing the consent.

Benefits:

The patients who are being recruited for this study have limited treatment options and have been suffering from frozen shoulder for years

Possible benefits include

1. Improvement in shoulder ROM
2. Improvement in VAS
3. Improvement in QOL
4. Reduced pain medication usage

Risks:

The procedure is relatively safe as the area near the CHL is relatively avascular. However, there is a risk a rupture of axillary artery. Care will be taken to ensure this does not happen by clear identification of the axillary artery by using USG.

There is a potential this procedure may not improve ROM in which case the study will be stopped, and the IRB will be informed immediately as an adverse event.

Potential for infection, although a minimally invasive procedure there will be a small incision on the skin with potential for infection. All care will be taken to perform the procedure in standard universal precautions. Post procedure the incision will be cleaned, and dressing applied. Standard wound care precautions will be given to the patients.

Study reimbursement: None

Statistical analysis:

Differences in VAS, opioid use, and QOL scores before and after the procedure will be compared using paired t-tests or Wilcoxon singed-rank tests.

Assume 30% of patients in the local anesthetic group will have at least a 100% improvement in range of motion one-month post treatment. With a sample size of 32 patients in the Tenex group and 16 patients in the local anesthetic group, the study will have 81.9% power to detect a difference of 45% in patients with at least a 100% improvement in range of motion between the Tenex group and local anesthetic group one-month post treatment using a two-sided Fisher's exact test at a 0.05 significance level.

Assume an attrition rate of 15%, 57 patients will be enrolled and randomized in a 2:1 ratio to receive either Tenex or local anesthetics.

Data analysis:

Simple descriptive statistics will be used in analysis of the data. The main primary outcome is the improvement in shoulder ROM and we expect to improve the ROM by at least 100 percent in external rotation. Differences in VAS, pain medication use, and QOL scores before and after the procedure will be compared using paired t-tests or Wilcoxon singed-rank tests.

Data Safety

The PI will give assurances of data safety as well as the timely report of any breach. The data will be stored on a password protected encrypted computer which is located in a locked room with access only to the PI and the research staff. The data reported will be deidentified and any chances of identifying information will be minimized. In addition, the data will be stored on an password protected excel file on the above password protected computers. The identifiers will be destroyed at the end of the study i.e., 3 years from the start of the study.

Subject Safety

In addition to following the inclusion/exclusion criteria, [REDACTED] will be available on the day of the procedure. He will not be scrubbed in to any other case and will be available for immediate back up in case of a medical or surgical complication on the day of the Tenex procedure. Please note he will also be in the same building.

DSMB and DSMP

Data safety monitoring board will be managed by [name], [name] and [name] [name]. All the three above Physicians are independent researchers and practicing clinicians with expertise in managing chronic pain at Montefiore. They are not associated with the study. [name] and [name] practice in Orthopedics and [name] practices Anesthesiology and pain medicine.

Any adverse events will be immediately reported to them in addition to IRB. They will regularly conduct data monitoring and safety visit every 6 months. In addition, they will assure the safety of research participants and continued relevance of the study question.

DSMP SCHEDULE

1. Adverse events reportable in 48 hours.

2. Safety monitoring every 6 months.
3. Independently report any safety concerns to IRB immediately at any point of the study.
4. They can stop the study if >40% of the study subjects have no improvement in ROM or worsening of ROM at 1-month visit
5. Study withdrawal criteria - worsening of the ROM>40 degrees from baseline in external rotation

References:

1. Wu, C.-H., Chen, W.-S., & Wang, T.-G. (2016). Elasticity of the Coracohumeral Ligament in Patients with Adhesive Capsulitis of the Shoulder. *Radiology*, 278(2), 458–464. doi: 10.1148/radiol.2015150888
4. Le, H. V., Lee, S. J., Nazarian, A., & Rodriguez, E. K. (2017). Adhesive capsulitis of the shoulder: review of pathophysiology and current clinical treatments. *Shoulder & elbow*, 9(2), 75–84. doi:10.1177/1758573216676786

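### No assessor is named and no blinding is described for the range-of-motion readings that decide the primary endpoint, which leaves the comparison open to observer bias

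*Combined protocol and SAP*

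**What the plan says.** - **Design.** The protocol calls the study a "Prospective double Arm randomized control trail". In the text available, blinding or masking of patient, operator, assessor or analyst is never mentioned.
- **Primary outcome.** "Improvement in shoulder range of motion (ROM) (external rotation) immediately post procedure by at least 100" per cent.
- **Measurement (Study Design).** "Subjects shoulder ROM, QOL, VAS and opioid usage will be assessed before and after the procedure in both the groups", and again at 1 month. No assessor or instrument is named.
- **Operator (Study Design).** The principal investigator "will also explain the procedure as he will be performing the procedure".
- **Other staff (Patient recruitment).** Patients are to be "consented, screened and enrolled into the study by the approved research staff". These staff are not assigned to measure ROM, and nothing says they are kept unaware of the arm.
- **Visible cue (Risks).** The procedure leaves a small skin incision, and "Post procedure the incision will be cleaned, and dressing applied". No incision, dressing or sham is described for the local anesthetic (LA) arm.
- **Crossover (Study Design).** LA patients may cross over to Tenex at the 1-month visit. The order of the offer and the ROM reading is not given.
- **Allocation list (end of document).** All 57 IDs are listed in blocks of three, followed by the key to A and B.

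**The concern.** A responder is defined by a measured angle crossing a cut-off, so readings near the cut-off decide the result. As written, nothing prevents the operator, who knows the arm, from taking the deciding reading. Anyone else who takes it could learn the arm from the dressing, from the crossover discussion or from the printed list.

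The between-arm contrast is the reason for randomising. If readings in one arm are shifted by a few degrees, a recorded difference cannot be cleanly attributed to the procedure. The same 1-month readings feed the data safety monitoring board's option to stop for lack of improvement, so monitoring rests on them too.

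Baseline matters as much as follow-up. Improvement of at least 100% means that the later reading is at least twice the baseline reading, so an error at baseline counts double.

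**Working it through.** **Inputs from the Power Analysis section.** 32 Tenex and 16 LA evaluable patients; 30% responders on LA; a difference of 45 points, so 75% on Tenex; two-sided Fisher's exact test at 0.05; 15% attrition; 57 enrolled at 2:1 (38 and 19).

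**Inputs that are assumptions.** The documents give no size for observer bias and no SD. I take a uniform over-reading of 5 or 10 degrees in the Tenex arm only, and a normal margin around the threshold with SD 10 to 30 degrees. The margin is the later reading minus twice the baseline reading, so the larger SDs are plausible.

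**Step 1: reproduce the plan's figure.** The plan states that "the study will have 81.9% power to detect a difference of 45" points. Summing binomial probabilities over every 32-by-16 table with Fisher p ≤ 0.05, at 75% against 30%, gives 81.95%, which agrees. Enrolment also agrees: 48 / 0.85 = 56.5, rounded up to 57.

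**Step 2: no effect and no bias.** With 30% in both arms, the same enumeration gives 3.1% significant in either direction and 1.4% favouring Tenex. The test is conservative at this size.

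**Step 3: add bias in degrees.** With a true rate of 30%, the threshold sits z(0.70) = 0.524 SD above the mean. An over-reading of b degrees gives

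recorded Tenex rate = P(Z > 0.524 − b/SD).

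For b = 5 and SD = 10: P(Z > 0.524 − 0.5) = P(Z > 0.024) = 49%. Each recorded rate is then compared with 30% on LA, using the exact probability that Fisher p ≤ 0.05 with Tenex higher, at 32 and 16:

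| SD (degrees) | Recorded rate, b = 5 | False positive, b = 5 | Recorded rate, b = 10 | False positive, b = 10 |
|---|---|---|---|---|
| 10 | 49% | 17.4% | 68% | 66.0% |
| 15 | 42% | 8.1% | 56% | 31.7% |
| 20 | 39% | 5.3% | 49% | 17.4% |
| 25 | 37% | 4.1% | 45% | 11.2% |
| 30 | 36% | 3.4% | 42% | 8.1% |

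**Step 4: the same in percentage points, without an SD.** At 32 and 16, false extra responders of 5, 10, 20 and 30 points in the Tenex arm give 3.0%, 5.9%, 19.2% and 43.1% favouring Tenex.

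**Step 5: baseline.** The responder rule is later reading − 2 × baseline ≥ 0. A 5-degree under-reading at baseline moves this margin by 2 × 5 = 10 degrees, so it has the effect of the b = 10 columns.

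**Step 6: the list.** Every block of three holds two A and one B. The printed list decodes every ID directly. Even without it, anyone who knows the block structure and the earlier assignments can often deduce the next one.

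**The case against.** Four objections have force.

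1. **Silence is not proof.** A reader might infer that nobody is blinded when ROM is measured. The documents do not say so; they are silent on who measures and what that person knows. The supportable statement is that no blinding is described and no assessor is named.
2. **The size is assumed.** A reader might infer that modest bias reliably produces a false positive. It does not. At SD 25-30 a 5-degree bias gives 3.4-4.1% favouring Tenex. That is above the no-bias 1.4% but still below 5%. The bias is also assumed to affect every Tenex patient and no LA patient. If the true gain were near the average 40 degrees in external rotation reported for the seven earlier patients, a few degrees would be unlikely to change the conclusion, but that gain is what the trial has to establish.
3. **The test is not tied to this endpoint.** The power statement begins "Assume 30% of patients in the local anesthetic group will have at least a 100% improvement in range of motion one-month post treatment", so Fisher's test is named for the one-month comparison. The primary outcome is immediate, and the analysis section plans simple descriptive statistics for it. A false positive primary result therefore presumes a test that the plan does not assign. The bias would still distort descriptive responder rates.
4. **Blind measurement by existing staff is not yet available.** A reader might infer that the research staff could simply take over. The documents do not place them outside the procedure room, they share access to the study data with the principal investigator, and the decoded list is in the protocol. They can be kept unaware only if the list is removed and the other safeguards are written in.

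Assessor blinding would also leave the patient's own knowledge of the arm untouched. None of this removes the gap itself.

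**Conclusion.** The point holds in a limited form. The plan names no ROM assessor and describes no blinding, while the operator, the dressing, the crossover offer and the printed list each offer a way for the arm to be known. Observer bias could therefore shift a thresholded primary endpoint.

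The size is illustrative only. With no true effect, 30% responders in both arms, 32 and 16 evaluable patients and a two-sided Fisher's test at 0.05, the rate favouring Tenex rises from 1.4% to about 3-17% for a 5-degree over-reading and about 8-66% for 10 degrees, over SD 10-30. Bias and SD are assumptions, and applying the test to the immediate endpoint is a further one. The documents do not show that anyone is in fact unblinded, that bias will occur, or that a false positive is likely. This is a cheap improvement to the plan, not a demonstrated error in its results.

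**What to change.** Add to Study Design:

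- Baseline ROM is recorded before the allocation is revealed to anyone involved in the reading.
- Post-procedure and 1-month ROM are measured by a member of the approved research staff who was not in the procedure room, has no access to the allocation list and is not told the arm. The operator does not take these readings.
- Patients in both arms leave the room with the same dressing over the site, and are asked not to disclose their arm.
- The 1-month ROM is measured before crossover is discussed.

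Remove the decoded randomization list from the protocol and have the in-house statistician hold it.

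**Cost.** Some scheduling effort, a dressing for LA patients and a protocol edit. No extra assessor, sham procedure or change in sample size is needed, and the calculated power stays at 81.9% with 32 and 16 evaluable. What remains is the patient's knowledge of the arm and its effect on effort during ROM testing, VAS and quality of life; the report should state this as a limitation.

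### Adverse events must be reported once known, but no visible text schedules anyone to look for them, so infection may be under-recorded, including after crossover to Tenex

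*Combined protocol and SAP*

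**What the plan says.** Under Study Design, the measurements are set out as "Subjects shoulder ROM, QOL, VAS and opioid usage will be assessed before and after the procedure in both the groups", followed by "These parameters will also be evaluated at the 1-month visits". Chart review supplies further data: "This includes patient medical, surgical history, medication history, other health conditions, demographics and exercise/physiotherapy sessions". Complications are not named in that list.

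The Risks section names two physical harms: "However, there is a risk a rupture of axillary artery" and "Potential for infection, although a minimally invasive procedure there will be a small incision on the skin with potential for infection". Against the first it offers identification of the artery by ultrasound. For the second it offers universal precautions, cleaning and dressing of the incision, and "Standard wound care precautions will be given to the patients". Subject Safety adds a clinician who is "available for immediate back up in case of a medical or surgical complication on the day of the Tenex procedure".

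The DSMB and DSMP section sends any adverse event to the board and the IRB at once. The DSMP schedule gives a 48-hour reporting limit, 6-monthly safety monitoring, and freedom for the board to take any safety concern to the IRB at any time. Its stopping item concerns range of motion (ROM): "They can stop the study if >40% of the study subjects have no improvement in ROM or worsening of ROM at 1-month visit".

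Statistical analysis and Data analysis cover ROM, VAS, opioid or pain-medication use and quality of life. Neither mentions adverse events.

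**The concern.** A duty to report an event begins only when someone knows of it. The plan says what happens next, but not who asks, when, with what definition or on what form. The procedure day and the 1-month visit are the only contacts stated, so about 4 weeks pass with none. A wound infection can begin and clear in that time.

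Local anesthetic patients may take Tenex at 1 month. This has two consequences. The first month is the only period in which the randomised arms can be described side by side for harms. And up to 19 further patients may be exposed to the device with no stated visit afterwards.

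At stake is whether a short list of events at the end of the trial can be read as evidence of safety for a procedure that the protocol itself calls novel. The analysis of the primary outcome is not affected.

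**Working it through.** **1. Number exposed.** Power Analysis gives 32 + 16 = 48 evaluable patients and 15% attrition. 48 / 0.85 = 56.5, rounded up to 57, which reproduces the stated enrolment. At 2:1 this is 38 Tenex and 19 local anesthetic. The randomization schedule agrees: 19 blocks of three, each with two Tenex and one control. If every control patient crosses over, 38 + 19 = 57 are exposed to Tenex.

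**2. Does any stated activity look for the named harms?**

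| Provision | Seeks or records infection? | Seeks or records rupture? |
|---|---|---|
| Measurements on the procedure day and at 1 month (Study Design) | Not listed | Not listed |
| Chart review (Study Design) | Not named; might surface through medication history or other conditions | Not named; might surface similarly |
| Wound-care instructions (Risks) | Advice to the patient; no check scheduled | Not applicable |
| Same-day back-up (Subject Safety) | Procedure day only | Likely to be noticed; no record form stated |
| Immediate or 48-hour reporting (DSMB and DSMP) | Once known | Once known |
| 6-monthly review (DSMP schedule) | Reviews what was reported | Reviews what was reported |

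No row schedules a question about adverse events. Infection is the more exposed of the two harms, because it can appear after the procedure day.

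**3. Illustration of size.** The documents visible here give neither a harm rate nor a capture rate, so both are assumptions. With true rate p, fraction captured c and n exposed, the chance of recording at least one event is 1 − (1 − p·c)^n.

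| n | p | c = 1 | c = 0.75 | c = 0.5 | c = 0.25 |
|---|---|---|---|---|---|
| 38 | 1% | 32% | 25% | 17% | 9% |
| 38 | 2% | 54% | 44% | 32% | 17% |
| 38 | 5% | 86% | 77% | 62% | 38% |
| 57 | 1% | 44% | 35% | 25% | 13% |
| 57 | 2% | 68% | 58% | 44% | 25% |
| 57 | 5% | 95% | 89% | 76% | 51% |

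For example, with n = 38, p = 1% and c = 0.5: 1 − 0.995^38 = 17%. These figures are meant for infection. Half capture is not a credible assumption for artery rupture.

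**4. How a record of zero would read.** With no events in 38 and full capture, the one-sided 95% upper limit is 1 − 0.05^(1/38) = 7.6%; for 57 it is 5.1%. If only half of events are captured, these limits bound p × 0.5, so the limits for p itself are about 15% (7.6% / 0.5) and 10% (5.1% / 0.5).

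**5. Can the control arm test for excess harm?** With 0 events in 19 controls, the two-sided Fisher p-value is 0.083 for 7 of 38 Tenex events and 0.042 for 8 of 38. So at least 8 events (8/38 = 21%) are needed. At a true rate of 5%, the chance of 8 or more among 38 is about 0.05%. A table by arm is descriptive only.

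**The case against.** The strongest reply is that safety does have a route. Any adverse event goes at once to the board and the IRB, the board meets on safety every 6 months, and it can raise any concern at any time. Patients return in person at 1 month to have the shoulder examined, and chart review could bring a treated infection to light. All of this stands. It limits the point to how events are found; it does not close the gap, because each of these provisions acts on what is already known or happens to surface.

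A reader might go further and infer that both named harms would be missed. The documents do not support that for rupture. It is treated as a procedural risk, with ultrasound identification of the artery and same-day back-up, and nothing suggests that it would go unnoticed. What is lacking is a systematic record.

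A reader might also infer that nobody will ask patients anything. The text is silent, and silence does not show that staff would not ask. Nor is all the text visible: what stood under the Safety data heading and the consent pages is not in the copy reviewed. Nothing is inferred from their absence, and prior event rates or contact instructions may appear there.

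Finally, a reader might see the ROM-based stopping item as contradicting the Risks section on infection and rupture. It does not. It is a lack-of-benefit criterion that says nothing about harms.

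**Conclusion.** The point holds as a gap in ascertainment. Reporting and review are provided for, but no visible text schedules active enquiry about adverse events, gives a contact between the procedure day and 1 month, or states a visit after crossover. Infection may be under-recorded as a result. Rupture is likely to be noticed but is not systematically recorded.

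The firm measure of size is the gap itself: about 4 weeks for each randomised patient, and open-ended for up to 19 who cross over. The probabilities above depend on assumed event and capture rates and show direction only. The claim that the randomised control would show whether Tenex causes excess harm should not be made, since 38 against 19 patients is far too few at plausible rates.

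There is a separate inconsistency on lack of ROM improvement. The Risks section says that the study will be stopped if the procedure does not improve ROM, whereas the DSMP schedule says of the board: "They can stop the study if >40% of the study subjects have no improvement in ROM or worsening of ROM at 1-month visit". One is mandatory without a threshold, the other discretionary with one.

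**What to change.** Add to Study Design, for both arms:

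- A fixed adverse-event question set (infection, bleeding or haematoma, new arm symptoms), with an incision check where there is an incision, on the procedure day and at the existing 1-month visit.
- One scripted telephone contact by existing research staff between those two visits.
- The same questions, call and a 1-month contact for patients who cross over to Tenex.

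Add to Data analysis a descriptive table of events by arm, with crossover exposures shown separately, for each 6-monthly board review and the final report. State that it is not a test of excess harm.

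The sponsor and the board should reconcile the Risks section and item 4 of the DSMP schedule on stopping for lack of ROM improvement.

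Cost: up to 57 + 19 = 76 calls, a 1-month contact for up to 19 crossover patients, one form and one table. Sample size, randomisation and the primary outcome do not change. The downside is that more minor events will be recorded, so the safety profile may look slightly less favourable.

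### Optional efficiency gain: at 32 v 16 the planned Fisher's exact test uses at most 3.2% of its 5% error allowance, and Boschloo's exact test would raise power from 81.9% to 85.6% within the same ceiling

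*Combined protocol and SAP*

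**What the plan says.** The Power Analysis section, repeated under Statistical analysis, gives the whole basis for the sample size:

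- Control rate: "Assume 30% of patients in the local anesthetic group will have at least a 100% improvement in range of motion", assessed one month after treatment.
- Effect and power: "81.9% power to detect a difference of 45% in patients with at least a 100% improvement", which makes the comparison 75% v 30%.
- Evaluable patients: 32 Tenex and 16 local anesthetic.
- Test: "one-month post treatment using a two-sided Fisher"'s "exact test at a 0.05 significance level".
- Enrolment: "Assume an attrition rate of 15%, 57 patients will be enrolled and randomized in a 2:1 ratio".

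Fisher's test is mentioned only in this power statement. The Statistical analysis and Data analysis sections name descriptive statistics and paired before-after tests, and no between-arm test of the responder outcome. Neither the conservatism of Fisher's test nor any unconditional exact test is discussed.

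**The concern.** Fisher's test conditions on the total number of responders as well as on the arm sizes. In a small trial each conditional distribution has few possible outcomes, so the attainable error usually falls well short of the nominal 5%. The unused error is lost power.

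The plan's own power statement treats the arms as two independent binomial samples with the arm sizes given. Under that model an unconditional exact test is also valid and can use more of the 5%. With 16 evaluable controls and stated power only 1.9 points above 80%, a test that gives more power from the same 48 patients is worth considering.

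**Working it through.** **Inputs.** From the Power Analysis section: n = 32 and 16; response rates 0.75 and 0.30; two-sided level 0.05.

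**Method.** Let x be responders among 32 and y among 16, which gives 33 × 17 = 561 possible tables.

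- Fisher's two-sided p-value for a table is the sum of the hypergeometric probabilities of all tables with the same responder total that are no more probable than the one observed. Reject if p ≤ 0.05.
- Power = Σ Bin(x; 32, 0.75) × Bin(y; 16, 0.30) over the rejected tables.
- True size at a common rate π = Σ Bin(x; 32, π) × Bin(y; 16, π) over the rejected tables. The maximum is taken over 1,999 values of π from 0.0005 to 0.9995.
- Boschloo's test rejects if Fisher's p ≤ c, where c is the largest cut-off that keeps the maximum size at or below 0.05.

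**The plan's figures reproduce.** Fisher's power is 0.8195, against the stated 81.9%. Enrolment is 48 / 0.85 = 56.5, rounded up to 57.

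**Results at 32/16**

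| | Fisher | Boschloo |
|---|---|---|
| Cut-off on Fisher's p | 0.05 | 0.0650 |
| Maximum true size | 3.22% (near π = 0.77) | 4.68% |
| Power, 75% v 30% | 81.9% | 85.6% |
| Power, 70% v 30% | 70.4% | 75.1% |
| Power, 65% v 30% | 57.1% | 62.3% |

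Boschloo's rejection region contains all of Fisher's tables plus 14 more, so under this model its power cannot be lower for any pair of rates. The gain at the design effect is 85.6 − 81.9 = 3.7 points. It is about 5 points for the two smaller effects.

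**Other evaluable splits, 75% v 30%**

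| Tenex/LA | Fisher | Boschloo | Gain (points) |
|---|---|---|---|
| 30/15 | 80.0% | 82.7% | 2.7 |
| 31/15 | 79.8% | 84.8% | 5.0 |
| 31/16 | 83.2% | 85.2% | 2.0 |
| 33/16 | 80.7% | 86.5% | 5.8 |
| 33/17 | 86.3% | 87.3% | 1.0 |
| 34/17 | 85.7% | 88.2% | 2.5 |
| 36/18 | 88.7% | 89.3% | 0.6 |
| 38/19 | 89.9% | 91.5% | 1.7 |

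Fisher's power moves up and down as patients are added: it is higher at 31/16 than at 32/16.

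**Conditional error.** Given the responder total, Boschloo's rejection rate at 32/16 can reach its cut-off of 6.5%. Fisher's is at most 5% for every total.

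**Comparator.** The unadjusted chi-square test has 87.4% power but a maximum size of 5.35%, so it breaks the 5% ceiling. Boschloo's test does not.

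**The case against.** The strongest case for leaving the plan alone is that nothing in it is wrong. Fisher's test is valid, familiar and correctly powered above 80%. That stands, and it limits this point to an optional improvement. A reader might infer that the trial is underpowered or uses the wrong test; the documents do not support that.

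A reader might also infer that the extra power is free in error rate. It is not. Boschloo's test gains power by spending error that Fisher's leaves unused. Only the nominal 5% ceiling is unchanged.

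Nor can the gain be read as a fixed saving in patients. If evaluable patients stay at exactly 2:1, Fisher's test needs 34/17, three more, to match 85.6%. Off that ratio, 33/17 (two more) already gives 86.3%. Attrition means the final split is unknown, and some plausible splits gain little.

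There is also a real difference of inferential position. Under a pure randomization argument with a sharp null hypothesis, the responder total is fixed and conditioning is natural. Boschloo's guarantee rests on independent binomial samples. The plan's power calculation uses the binomial model, so the proposal is consistent with it, but a statistician who prefers conditional inference can reasonably keep Fisher's test.

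Finally, the change cannot be made in isolation. The primary outcome is set immediately after the procedure, while the power statement concerns one month, and no between-arm test appears in the analysis text. Those are separate matters. They leave this calculation unchanged, but they must be reconciled.

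**Conclusion.** The point holds as a cheap, optional improvement. At 32/16 and 75% v 30%, Boschloo's test gives 85.6% power against 81.9%, with maximum unconditional size 4.7% against 3.2%. The gain was 0.6 to 5.8 points in the splits checked, and 1.7 points if all 57 patients are evaluable.

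These figures rest on the plan's own response rates, on independent binomial sampling, and on the form of Fisher's two-sided p-value that reproduces 81.9%. If the one-sided p-value is doubled instead, Fisher's power is 79.3% and Boschloo's 85.8%, so the choice of Fisher variant should be stated as well.

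**What to change.** Before outcome data are seen, add to the Statistical analysis section:

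- The between-arm comparison of the proportion with at least 100% improvement in range of motion at one month, the comparison that the power statement covers, is tested with Boschloo's exact unconditional test at two-sided 0.05, with tables ordered by the two-sided Fisher p-value.
- The test is computed at the actual evaluable arm sizes. The 0.065 cut-off applies only at exactly 32/16 and should not be written in as a rule.
- Fisher's two-sided p-value is reported as supportive.

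Restate power as 85.6% at 32/16, in both places where 81.9% appears. Say openly that the maximum type I error rises from 3.2% to 4.7%, and that the 5% guarantee is unconditional (up to 6.5% given the responder total at 32/16).

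The cost is a few sentences and perhaps software other than the package named for randomization. No patient, visit or measurement is added. Reconcile the immediate primary outcome with the one-month power statement at the same time, so that the named test is attached to a settled endpoint.
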